# 5.5 Dose Limiting Toxicities

A DLT is defined as a clinically relevant AE or abnormal laboratory value of CTCAE  $\geq$ Grade 3 assessed as unrelated to disease, disease progression, inter-current illness or concomitant medications, which occurs within the first cycle (21 days) of treatment with KY1044 as single agent or in combination with atezolizumab during the dose escalation part of the study, with the exceptions described in Table 5-4.

National Cancer Institute CTCAE Version 5.0 will be used for all grading. For dose-escalation decisions, DLTs will be considered by the SRC. As meeting the criteria of DLT (please refer to Table 5-4) will be also collected in Cycle 2 and later cycles and will be considered by the SRC for ongoing safety decision.

The Investigator must notify the Sponsor immediately of any unexpected CTCAE v5  $\geq$ Grade 3 Aes or laboratory abnormalities. Prior to enrolling patients into a higher dose level, all CTCAE v5  $\geq$ Grade 2 will be reviewed for all patients at the current dose level and will also be considered for further dose escalation.

 Table 5-4:
 Criteria for Defining Dose Limiting Toxicities

For dose escalation and cohort expansion, DLT will be adjudicated as follows: Any Grade 4 Aes will be adjudicated DLTs with the exception of:		
Neutropenia lasting <72 hours that is not associated with fever or other clinical symptoms.		
Lymphopenia		
Electrolyte abnormalities that are not associated with clinical sequelae and are corrected with appropriate management or supplementation within 72 hours of the onset.		
Any Grade 3 Aes will be adjudicated as DLTs except for:		
Nausea and vomiting persisting for <2 days after optimal anti-emetic therapy.		
Thrombocytopenia without significant bleeding (including platelet transfusions).		
Diarrhea persisting for <2 days after optimal anti-diarrhea treatment.		
Hypertension persisting <7 days after treatment.		

Infection or fever in the absence of neutropenia persisting <5 days.
Rash or photosensitivity persisting <7 days after treatment.
Fatigue lasting <7 days.
LFT elevations (AST/ALT) persisting <7 days after treatment with corticosteroids.
Immune-related adverse events persisting <7 days after treatment with corticosteroids.
The following Grade 2 Aes will be adjudicated as DLTs:
Total bilirubin CTCAE v5 ≥Grade 2 with ALT/AST CTCAE v5 ≥Grade 2.
Pneumonitis persisting >7 days despite treatment with corticosteroids.
Eye pain or reduction of visual acuity that does not respond to topical therapy and does not improve to Grade 1 severity within 2 weeks of the initiation of topical therapy OR requires systemic treatment.
Other clinically significant toxicities (cardiotoxicity, neurotoxicity) including a single event or multiple occurrences of the same event that lead to a dosing delay of >7 days in Cycle 1.

AE=adverse event; ALT=alanine aminotransferase; AST=aspartate aminotransferase; CTCAE v5=Common Terminology Criteria for Adverse Events Version 5; DLT=dose limiting toxicity; LFT=liver function test.

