# 5.6 Dose Modifications and Management of Toxicities

#### 5.6.1 Dose Modifications and Dose Delays

For patients who do not tolerate the protocol -specified dosing schedule, dose adjustments are permitted to allow the patient to continue the study treatment. The following guidelines must be followed:

- If a patient experiences an AE meeting the criteria for a DLT as outlined in Section 5.5 (including events occurring after Cycle 1), treatment should be withheld. Dose modifications for toxicities related to the study medication are summarized in Table 5-5. Following resolution of the toxicity to Grade 1 or to the patient's baseline value (as outlined in the safety management guidelines in Table 5-5), the patient may resume study treatment at the same or the next lower dose level (Table 5-2, Table 5-3) assessed to be safe (on the same dosing schedule [administration every 21 days]), if there is no evidence of disease progression as per iRECIST.
- For patients in the dose escalation part of the study receiving KY1044 in combination with atezolizumab, the KY1044 dose level will be lowered to the next lower dose level. **Dose reductions of atezolizumab are not allowed.**
- The decision to resume treatment with KY1044 as single agent or in combination with atezolizumab following the occurrence of a DLT is at the discretion of the Investigator. If the Investigator considers it to be in the patient's best interest to resume therapy before the toxicity has resolved to Grade 1, or to resume without dose reduction, this may be permitted on a case by case basis, following discussion with the Medical Monitor.
- Dose reductions for KY1044 to below 0.24 mg (less than starting dose -1) are not permitted.
- If a patient who misses more than one consecutive dose due to study treatment -related toxicity experiences clinical benefit, and in the opinion of the Investigator it is in the patient's best interest to remain on study, then the patient may continue treatment after discussion with the Medical Monitor.

- Patients who discontinue study treatment for a study related AE or a study -related abnormal laboratory value must complete their EOT visit and safety followup procedures as described in Section 5.6.2 below and be followed up for PFS and survival (please refer to Section 8.2.2).

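### Table 5-4 exempts lymphopenia, brief afebrile neutropenia and corrected electrolyte changes from being DLTs at Grade 4 but not at Grade 3, so the milder event can count when the more severe one does not

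*Protocol*

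**What the plan says.** Protocol 5.5 opens with a general definition: "A DLT is defined as a clinically relevant AE or abnormal laboratory value of CTCAE" Grade 3 or higher, "assessed as unrelated to disease, disease progression, inter-current illness or concomitant medications", occurring in the first 21 days, subject to the exceptions in Table 5-4.

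Table 5-4 then sets rules by grade. Its scope line is "For dose escalation and cohort expansion, DLT will be adjudicated as follows".

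- **Grade 4:** "Any Grade 4 Aes will be adjudicated DLTs with the exception of" three events: neutropenia under 72 hours without fever or other symptoms; lymphopenia, with no condition; and electrolyte abnormalities without sequelae that are corrected within 72 hours.
- **Grade 3:** "Any Grade 3 Aes will be adjudicated as DLTs except for" nine items: nausea and vomiting, thrombocytopenia, diarrhea, hypertension, infection or fever, rash or photosensitivity, fatigue, liver enzyme elevations and immune-related events. Each carries its own condition.

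Protocol 5.6.1 says that for "an AE meeting the criteria for a DLT as outlined in Section 5.5 (including events occurring after Cycle 1), treatment should be withheld". It continues: "Dose modifications for toxicities related to the study medication are summarized in Table 5-5". The lymphopenia row of Table 5-5 maintains the dose at Grade 3 or lower, delays a Grade 4 event until it is back to Grade 3 or lower, and does not require discontinuation.

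**The concern.** A more severe laboratory event should not be easier to excuse than a milder one of the same kind. Here the three exemptions stop at Grade 4, nothing carries them down to Grade 3, and no reason is given.

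Cycle 1 DLT incidence is a Phase 1 primary endpoint (Protocol 2.2.1), is counted in SAP 10.7.1, is reported by dose level (SAP 10.0) and is what enters the mTPI-2 decision table (Protocol 9.1.1). A literal count could include Grade 3 laboratory events and omit their Grade 4 forms. It could also hold back escalation or lower the declared MTD.

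Lymphopenia adds a dosing question, because meeting the DLT criteria triggers the hold in 5.6.1 while the specific row in Table 5-5 continues dosing.

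**Working it through.** **1. The two lists side by side (Table 5-4).**

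| Event | Grade 4 | Grade 3 |
|---|---|---|
| Lymphopenia | Exempt, no condition | Not named, so a DLT |
| Neutropenia <72 h, no fever or symptoms | Exempt | Not named, so a DLT |
| Electrolyte change, no sequelae, corrected within 72 h | Exempt | Not named, so a DLT |

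Neutropenia is mentioned in the Grade 3 list only as a limit on the infection and fever exception. The ninth exception, "Immune-related adverse events persisting <7 days after treatment with corticosteroids", could in principle reach a cytopenia treated with steroids. The lymphopenia and neutropenia rows of Table 5-5 prescribe no steroids, so it does not fill the gap.

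**2. What the general definition does.** The clinical-relevance condition in 5.5 applies formally to all three events. The neutropenia and electrolyte exemptions already describe short events without symptoms or sequelae, which are the ones most likely to be judged not relevant. Protocol 6.5.6 also requires a single asymptomatic laboratory abnormality to be repeated before it becomes an AE. Lymphopenia is different: at Grade 4 it is exempt even if clinically relevant, while a clinically relevant Grade 3 lymphopenia counts.

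**3. Dosing for Grade 3 lymphopenia that meets the DLT criteria.** Protocol 5.6.1, general sentence: withhold. Table 5-5 row: maintain the dose. 5.6.1 states resumption at Grade 1 or baseline; the row accepts Grade 3 even after a Grade 4 event.

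**4. Sensitivity of the endpoint and the decision to one counted event.** Inputs from Protocol 9.1 and Appendix 4: target 0.30, e1 = e2 = 0.05, sub-intervals of length 0.10. Assumed for the recomputation: Beta(1,1) prior, and a dose excluded when P(p > 0.30) > 0.95. As a check, this gives De-escalate for 3 DLTs in 6 patients, as Appendix 4 states.

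| Patients | Decision for 0, 1, 2, … DLTs | Steps that change | Incidence shift, 1/n |
|---|---|---|---|
| 3 | E, S, D, DU | 3 of 3 | 33.3 points |
| 6 | E, E, S, D, DU, DU, DU | 3 of 6 | 16.7 points |
| 9 | E, E, E, S, D, then DU for 5 to 9 | 3 of 9 | 11.1 points |

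E = Escalate, S = Stay, D = De-escalate, DU = De-escalate and never reuse the dose. Every change is towards the stricter decision.

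**5. Illustration with assumed rates.** Let g be the share of patients with a counted Grade 3 event of these types, independent of other DLTs with rate p. Then P(at least one in 3) = 1 − (1 − g)³. P(Escalate after 3) = [(1 − p)(1 − g)]³, so for any p the multiplier is (1 − g)³.

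| Assumed g | P(at least one in 3) | Multiplier on P(Escalate) |
|---|---|---|
| 2% | 5.9% | 0.94 |
| 5% | 14.3% | 0.86 |
| 10% | 27.1% | 0.73 |

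**The case against.** The best defence is that Table 5-4 should be read under its parent definition. Brief, asymptomatic neutropenia and promptly corrected electrolyte changes would often fail the clinical-relevance condition, and the SRC uses the mTPI-2 table alongside other data (Protocol 5.4.5.2). This stands for many individual events. It does not repair the rule: the Grade 3 line says any AE and does not repeat the condition, and lymphopenia is exempt at Grade 4 whatever its relevance.

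On dosing, 5.6.1 points to Table 5-5 in its next sentence. Its third bullet leaves resumption to the Investigator and permits it before Grade 1, case by case, after discussion with the Medical Monitor. That disposes of most of the resumption difference. It does not authorise dosing through without an initial hold, so the mismatch on withholding remains.

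Three further points stand:

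- The figures above apply to any DLT in a small cohort and do not measure how often this problem arises.
- The SAP already tabulates Grade 3 or higher TEAEs and worst laboratory grades (10.7.1, 10.7.3), so such events will be visible by dose level, though not as an alternative DLT count.
- Protocol version 2.0 changed the DLT criteria at the FDA's request (Appendix 5). The documents do not show what was asked, so it is unknown whether the stricter Grade 3 list was intended.

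**Conclusion.** The inversion is real in the text. It is unconditional for lymphopenia and conditional for the other two events. It is a rule that gives the wrong ordering, in a primary endpoint and a decision input, and not merely missing detail.

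The error is conservative: over-counted DLTs, possibly slower escalation or a lower MTD. One counted event shifts incidence by 33.3, 16.7 or 11.1 points with 3, 6 or 9 patients. The 2% to 10% rates are assumptions, and independence from other DLTs is assumed too; the documents support no frequency.

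A reader might infer any of the following, and none is supported:

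- **That patients were exposed to excess toxicity.** The unmatched exemptions make the Grade 3 rule stricter, not looser.
- **That escalation decisions or the MTD were in fact distorted.** No event data are given, and the SRC could depart from the table.
- **That all three events are equally clear inversions.** Only lymphopenia is free of conditions.
- **That 5.6.1 and Table 5-5 conflict throughout.** The conflict shown here is confined to the initial hold and the default resumption wording for lymphopenia.

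**What to change.** **Protocol.** State in Table 5-4 that the three Grade 4 exceptions, with the same conditions, also apply at Grade 3. State in 5.6.1 that the Table 5-5 lymphopenia row governs withholding and resumption for lymphopenia. The second change matters after escalation too, because 5.6.1 covers events after Cycle 1.

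**SAP.** The November 2021 protocol already selects TNBC and HNSCC for Phase 2, and SAP version 3.0 is dated March 2024, so the rewording may come too late for escalation. If escalation is complete, keep the DLT adjudication as it was made as primary. In SAP 10.7.1, before database lock, flag any adjudicated Cycle 1 DLT that was Grade 3 lymphopenia, brief afebrile neutropenia or a corrected electrolyte change. Show DLT incidence by dose level with and without those events. If there are none, one sentence saying so closes the matter.

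**Cost.** Two wording changes, one flag and one extra summary line; no new patients or visits. The flag needs a small amount of clinical review of DLTs already adjudicated, using AE start and stop dates. Scheduled laboratory grades alone will not do: Phase 1 Cycle 1 hematology falls on Days 1, 2, 8 and 15 and chemistry on Days 1, 8 and 15, which often cannot establish a duration under 72 hours.

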# 5.6 Dose Modifications and Management of Toxicities

#### 5.6.1 Dose Modifications and Dose Delays

For patients who do not tolerate the protocol -specified dosing schedule, dose adjustments are permitted to allow the patient to continue the study treatment. The following guidelines must be followed:

- If a patient experiences an AE meeting the criteria for a DLT as outlined in Section 5.5 (including events occurring after Cycle 1), treatment should be withheld. Dose modifications for toxicities related to the study medication are summarized in Table 5-5. Following resolution of the toxicity to Grade 1 or to the patient's baseline value (as outlined in the safety management guidelines in Table 5-5), the patient may resume study treatment at the same or the next lower dose level (Table 5-2, Table 5-3) assessed to be safe (on the same dosing schedule [administration every 21 days]), if there is no evidence of disease progression as per iRECIST.
- For patients in the dose escalation part of the study receiving KY1044 in combination with atezolizumab, the KY1044 dose level will be lowered to the next lower dose level. **Dose reductions of atezolizumab are not allowed.**
- The decision to resume treatment with KY1044 as single agent or in combination with atezolizumab following the occurrence of a DLT is at the discretion of the Investigator. If the Investigator considers it to be in the patient's best interest to resume therapy before the toxicity has resolved to Grade 1, or to resume without dose reduction, this may be permitted on a case by case basis, following discussion with the Medical Monitor.
- Dose reductions for KY1044 to below 0.24 mg (less than starting dose -1) are not permitted.
- If a patient who misses more than one consecutive dose due to study treatment -related toxicity experiences clinical benefit, and in the opinion of the Investigator it is in the patient's best interest to remain on study, then the patient may continue treatment after discussion with the Medical Monitor.

- Patients who discontinue study treatment for a study related AE or a study -related abnormal laboratory value must complete their EOT visit and safety followup procedures as described in Section 5.6.2 below and be followed up for PFS and survival (please refer to Section 8.2.2).
- Active SARS-Cov-2 infections in patients enrolled into the study should be treated as Aes. This also applies to any other concurrent illnesses, which might occur during the study. Treatment interruption of KY1044 as single agent and in combination with atezolizumab should be considered on an individual patient basis after discussion with the Medical Monitor.
- All interruptions or change to study drug administration must be recorded in the patient's hospital files and eCRF.

# 5.6.2 Follow-up for Toxicities

- The emergence of irAEs may be anticipated based on overall experience in clinical studies with similar immunomodulators.
- An irAE is a clinically important AE of unknown etiology associated with the study • drug exposure. IrAEs are typically low grade and self-limited, often occurring after multiple doses, and most frequently involving the GI tract (diarrhea/colitis), skin (rashes), liver (hepatitis), and endocrine systems (a variety of endocrinopathies) and lung (pneumonitis). Serologic, histologic (tumor sample) and immunological assessments should be performed as deemed appropriate by the Investigator, to verify the immune related nature of the AE, and exclude the neoplastic, infectious or metabolic origin of the AE. Management Algorithms (Table 5-5) have been developed to assist Investigators in assessing and managing the following groups of Aes: Infusion reactions, Hematological, Cardiological, GI, Renal, Pulmonary, Hepatic, Endocrinopathy, Dermatological, Neurological, Ophthalmological, and Rheumatological Aes.
- Patients whose treatment is interrupted or permanently discontinued due to an irAE, AE or clinically significant laboratory value, must be followed-up at least once a week (or more frequently if required by institutional practices, or if clinically indicated) for 4 weeks, and subsequently at approximately 4-week intervals, until resolution or stabilization of the event, whichever comes first. Appropriate clinical experts should be consulted as deemed necessary.
- In case of a suspected irAE, the relevant immunological assessments (eg, rheumatoid factor, anti-deoxyribonucleic acid (DNA) Ab, etc.) should be performed and guidelines as outlined in Table 5-5 (and laboratory assessments Section 6.5.6) should be followed.

All patients must be followed up for irAEs, Aes and SAEs for 90 days following the last dose of KY1044 as single agent or in combination with atezolizumab.

Table 5-5 outlines the follow-up evaluation recommended for selected toxicities. For any irAEs/Aes Grade 1 and/or Grade 2, treatment with KY1044 and atezolizumab (if applicable) should be maintained at the determined dose and schedule, unless otherwise specified in Table 5-5.

10-Nov-2021 Version number: 1

# Table 5-5: Management of Toxicities Defined as Study Treatment-related Only

Infusion Reaction and Cytokine Release Syndrome (CRS)					
Grade	CTCAE description	Management	Specialist referral		
2	Mild transient reaction; infusion interruption not indicated; intervention not indicated Therapy or infusion interruption indicated but responds promptly to symptomatic treatment (eg, antihistamines, NSAIDS, narcotics, IV fluids); prophylactic medications indicated for ≤24 hours	
 
Drug infusion rate may be decreased, or infusion temporarily interrupted, until resolution of the event
 
Consider reducing the rate of infusion upon re-initiation or subsequent infusions
 
NSAIDs (eg, acetaminophen), antihistamines, opioids, and corticosteroids may be used per Investigator/ institutional guidelines
 
Consider premedication for subsequent infusions per Investigator/ institutional guidelines
 
If CRS is suspected (very high fever and precipitous drops in blood pressure, myalgia, change in mental status) treat with corticosteroids according to local standards (and/or with tocilizumab)
 
Take blood for cytokine measurements immediately after the occurrence of the AE and during treatment
 
			
3	Prolonged (eg, not rapidly responsive to symptomatic medication and/or brief interruption of infusion); recurrence of symptoms following initial improvement; hospitalization indicated for clinical sequelae	
 
Permanently discontinue ICI
 
For severe/life-threatening reactions, manage the patient as clinically appropriate (eg, antihistamines, oxygen, fluids, opioids, corticosteroids, bronchodilators, etc.) per Investigator/institutional guidelines
 
Provide supplemental oxygen, fluids, and other resuscitative measures and/or measures for symptomatic relief (see under Grade 2, above) as needed. Monitor vital signs (eg, BP, HR, respiration, and temperature) every 15 ±5 minutes until resolution
 
	✓ Refer to allergist to prevent future reactions		
4	Life-threatening consequences; urgent intervention indicated				

Amended Clinical Trial Protocol 07 KY1044/SAR445256-KY1044-CT01/TCD17370 - alomfilimab 10-Nov-2021 Version number: 1

HAEMATOLOGICAL					
Grade	CTCAE description	Management	Specialist referral		
Anemia	Anemia				
1	Hgb <lln-10.0 b="" dl;<="" g=""> (<lln-6.2 l;
<lln-100 g="" l)<="" td="">Monitor closely while continuing ICI	1	</lln-100></lln-6.2></lln-10.0>	Monitor closely while continuing ICI	1		
2	Hgb <10.0–8.0 g/dL; (<6.2–4.9 mmol/L; <100-80 g/L)	

Monitor closely while continuing ICI

Evaluate for possible causes and refer to hematology if no obvious cause if identified

	1		
3	Hgb <8.0 g/dL; (<4.9 mmol/L; <80 g/L;) transfusion indicated	
 
Hold ICI
 
Consider Coombs testing and evaluation for hemolytic anemia
 
Consider re-treating with ICI if hemolytic anemia responds promptly (within a few days) to corticosteroids
 
	s		
4	Life-threatening consequences; urgent intervention indicated	Permanently discontinue ICI	✓		

 
Notes:
 
No firm recommendations for corticosteroid management are provided here as treatment should be individualized.
 
If unexplained anemia does not respond to steroids, consider bone marrow biopsy
 
					
Neutropenia (ANC)					
3	ANC <1000-500/mm 	• Dose delay for study treatment-related Grade 3 until resolved to ≤Grade 1	1		
4	ANC <500/mm 	• Discontinue for study treatment-related Grade 4 >7 days duration	1		
Febrile neutropenia					
3 4	ANC <1.0x10  /L, fever ≥38.5°C	
 
Dose delay for study treatment-related Grade 3 until resolved to ≤Grade 1
 
Discontinue for study treatment-related Grade 4
 
	1		
Thrombocytopenia					
3	PLT <50,000-25,000/mm 	
 
Dose delay for study treatment-related Grade 3 until resolved to ≤Grade 1
 
Discontinue for study treatment-related Grade 3 >7 days or associated with bleeding
 
	1		

Property of the Sanofi Group - strictly confidential

PAGE 69 OF 217

#### Amended Clinical Trial Protocol 07

KY1044/SAR445256-KY1044-CT01/TCD17370 - alomfilimab

10-Nov-2021 Version number: 1

4	PLT <25,000/mm 	Discontinue for study treatment-related Grade 4	1	
Notes: Progressive or Grade 3 unexplained thrombocytopenia: consider work up for autoimmune disease and rule out DIC or other cause of thrombocytopenia that may be related to underlying disease Precipitous development of thrombocytopenia: consider steroid intervention pending clinical condition (brain metastases, colitis, etc.) and evaluate for immune-mediated thrombocytopenia Permanently discontinue ICI for clinically significant, steroid refractory ICI-associated thrombocytopenia				
Lymph	openia			
3	<0.5-0.2x10  /L	• Maintain dose level for study treatment-related ≤Grade 3		
4	<0.2x10  /L	• Dose delay for study treatment-related Grade 4 until resolved to ≤Grade 3		
		• Study treatment-related Grade 4 lymphopenia or leukopenia does not require discontinuation		
RENAI	_			
Grade	CTCAE description	Management	Specialist referral	
Nephrit	is (Creatinine increase)			
1	Creatinine >1.5–2xabove baseline; >0.3 mg/dL	• Continue ICI but initiate work-up to evaluate possible causes and monitor closely		
2	Creatinine >2-3xabove baseline	• Dose delay for study treatment-related ≥Grade 2 until resolved to ≤Grade 1		
		• Start corticosteroids (Note 3)		
		Discontinue ICI for persistent or recurrent elevation		
3	Creatinine >3xbaseline or	Hold ICI		
	>4 mg/dL Hospitalization indicated	• Consider resuming treatment if Grade 3 resolves (Note 2) and cause of event is confirmed. Timing of event and response to treatment should be considered in making a decision		
		

Start corticosteroids (Note 3)

Discontinue ICI for persistent or recurrent elevation

		
4	Creatinine >6.0xULN Life threatening consequences dialysis indicated	
 
Discontinue for study treatment-related Grade 4
 
Start corticosteroids (Note 3)
 
	✓	

Property of the Sanofi Group - strictly confidential

PAGE 70 OF 217

Amended Clinical Trial Protocol 07 KY1044/SAR445256-KY1044-CT01/TCD17370 - alomfilimab 10-Nov-2021 Version number: 1

Notes:

1. Grades are those listed under 'acute kidney injury' in CTCAE.

- 2. Consider using increase from baseline rather than absolute value for creatinine monitoring, especially in patients with primary renal carcinoma or other baseline renal conditions.
- 3. For persistent creatinine elevation ≥Grade 2 with no other identifiable cause, start corticosteroids. Dose and schedule should be individualized and based on grade. Taper corticosteroids when creatinine improves to Grade 1.

НЕРАТ	TIC				
Hepatit	Hepatitis				
Grade	CTCAE description	Management	Specialist referral		
1	AST, ALT >ULN-3xULN; total bilirubin >ULN- 1.5xULN	
 
Continue ICI
 
CMP or hepatic function panel once weekly
 
If liver enzyme and function tests are stable, reduce frequency of blood tests
 
			
2	AST, ALT >3-≤5xULN; total bilirubin >1.5-≤3xULN	
 
Hold ICI
 
Rule out viral hepatitis, autoimmune disease, biliary obstruction, new metastasis or thrombosis
 
Start prednisone 0.5-1 mg/kg/day (or equivalent dose of methylprednisolone) with 4-week taper
 
Monitor CMP twice a week
 
Liver biopsy is optional
 
Resume ICI when corticosteroid taper to 10 mg/day (toxicity Grade ≤1)
 
			
3 and 4	AST, ALT >5xULN; total bilirubin >3xULN	
 
Permanently discontinue ICI
 
Monitor CMP every 1–2 days
 
Start prednisone 1–2 mg/kg/day 
 
If refractory after 3 days, consider mycophenolate
 
 
 
If liver enzymes improve, taper corticosteroid over 4 weeks
 
Consider liver biopsy
 
 a is due to the indirect (non-conjugated) component only, and hemolysis as the etiology has been ruled of the indirect (non-conjugated) component only.	out as per institutional		
guidelin	guidelines (eg, review of peripheral blood smear and haptoglobin determination), then reduce one dose level and continue treatment at the discretion of the Investigator.				

Property of the Sanofi Group - strictly confidential

PAGE 71 OF 217
Amended Clinical Trial Protocol 07 KY1044/SAR445256-KY1044-CT01/TCD17370 - alomfilimab 10-Nov-2021 Version number: 1

Asymptomatic amylase and/or lipase elevation			
3 4	>2.0-5.0xULN >5.0xULN	Any study treatment-related Grade $\geq 3$ isolated amylase or lipase abnormality that is not associated with symptoms or clinical manifestations of pancreatitis does not require dose delay or discontinuation. The Kymab Medical representative should be consulted for such amylase or lipase abnormalities.	
Note: A and/or li	CT scan or other imaging study to pase. If asymptomatic Grade 2 ele	assess the pancreas, liver, and gallbladder must be performed within 1 week of the first occurrence of any vations of lipase and/or amylase occur again at the reduced dose, patients will be discontinued permanently	$r \geq$ Grade 3 of amylase from study treatment.
CARDI	AC		
Grade	CTCAE description	Management	Specialist referral
1	Abnormal cardiac biomarker testing, including abnormal ECG	
 
Recommend baseline ECG and cardiac biomarker assessment (BNP, troponin) to establish if there is a notable change during therapy
 
Mild abnormalities should be observed closely during therapy
 
	√ if abnormal
2	Abnormal screening tests with mild symptoms	
 
Control cardiac diseases (eg, heart failure, atrial fibrillation) optimally
 
Control cardiac disease risk factors proactively (including hypertension, hyperlipidemia, discontinue smoking, and monitor diabetes)
 
	$\checkmark$
3	Moderately abnormal testing or symptoms with mild activity	
 
BNP >500 pg/mL, troponin >99% institutional normal, new ECG findings (QTc prolongation, new conduction disease, or ST-T wave changes)
 
Consider withholding ICI 
 
If a period of stabilization is achieved and definite cardiac toxicity was not identified, it may be reasonable to consider re-challenging the patient with ICI, with heightened monitoring.
 
 
 
If confirmed cardiac injury or decompensation, hold ICI therapy until stabilized.
 
Optimally treat identified cardiac conditions
 
Consider corticosteroids if myocarditis suspected (Note 2)
 
	$\checkmark$
4	Moderate to severe decompensation, intravenous medication or intervention required, life threatening conditions	
 
Permanently discontinue ICI
 
If myocarditis is identified, consider high-dose corticosteroids (1 mg/kg methylprednisolone (IV) for at least several days) until improved to Grade ≤1, after that consider at least 4–5 weeks of tapering doses (Note 2).
 
Add additional immunosuppressive agents in severe refractory cases.
 
	✓

Property of the Sanofi Group - strictly confidential

PAGE 72 OF 217

## Amended Clinical Trial Protocol 07

KY1044/SAR445256-KY1044-CT01/TCD17370 - alomfilimab

10-Nov-2021 Version number: 1

		• Give additional supportive treatments, including appropriate treatment of heart failure. Additional treatment of detected cardiac conditions should be provided.*		
Notes: 1. Grad 2. Patie of try basis cardi * Other	
 
Notes:
 
1. Grades outlined here are not drawn from CTCAE (see Putzanov et al "cardiovascular adverse events")
 
2. Patients with confirmed myocarditis (or in cases of reasonable suspicion) should receive emergent high-dose corticosteroids. Until data are available (eg, cut-off levels of troponin) to determine when to start corticosteroids in patients with possible (as opposed to confirmed) myocarditis, this decision should be made on a case by case basis. The importance of active, ongoing consultation with a cardiologist to discuss the benefit/risk of continuing ICI therapy, starting corticosteroids, or instituting other cardiac treatments, cannot be overstated.
 
* Other therapies for management of myocarditis or pericarditis (viral based therapy, immunoglobulins, or plasmapheresis) are speculative at this point in time.
 
			
ENDOC				
Grade	CTCAE description*	Management	Specialist referral?	
1 2 3	Asymptomatic or mild symptoms; clinical or diagnostic observations only; intervention not indicated Moderate; minimal, local or non-invasive intervention indicated; limiting age appropriate instrumental ADL Severe or medically significant but not immediately life- threatening; hospitalization or prolongation of existing hospitalization indicated; disabling; limiting self-care	
 
Hold ICI if ≥Grade 2 irAE until work up is completed and appropriate hormone replacement is started
 
If central adrenal insufficiency: start physiologic steroid replacement: Hydrocortisone ~10 mg/m^2 (HC 15 mg am, 5 mg at 3 pm)
 
Periodic assessment (eg, every 3 months in the first year, every 6 months thereafter): clinical monitoring and repeat hormone levels (am cortisol and ACTH and/or low dose cosyntropin stimulation test) to assess recovery
 
If central hypothyroidism: start thyroid hormone (levothyroxine 1 mcg/kg)
 
Repeat thyroid function testing 6-8 weeks after initiation of thyroid hormone and then periodically (eg, every 3 months in the first year and every 6 months thereafter) to assess recovery
 
If central hypogonadism, repeat hormone levels in 2–3 months and consider testosterone in men or HRT in women if appropriate for cancer type
 
	✓ ✓	
4	ADL Life-threatening consequences; urgent intervention indicated	
 
For severe/life-threatening symptoms such as adrenal crisis, severe headache, visual field deficiency:
 
Hospitalize as appropriate.
 
High dose corticosteroid (prednisone 1 mg/kg/day) (or equivalent dose of methylprednisolone) in the acute phase, followed by taper over 1 month.
 
Adrenal crisis should be managed per standard guidelines.
 
		

Property of the Sanofi Group - strictly confidential

PAGE 73 OF 217

